Sleep measurements and renal function: Preliminary evidence suggests that disruption of the sleep-wake cycle promotes the development of four major chronic kidney disease (CKD) risk factors: **hypertension, diabetes, obesity and increased** renin-angiotensin-aldosterone system **activation (RAAS)**, thereby leading to a more rapid decline in glomerular filtration rate (GFR) and increased proteinuria (**Figure 1**). Individuals who report sleep duration 5 hours or less per night are 20% more likely to develop hypertension than those sleeping 7 hours per night.¹⁷ Similarly, in detailed polysomnography (PSG) studies, elderly men with reduced duration of "restorative" or "deep" slow wave sleep (SWS or stage N3 sleep) had an increased risk of incident hypertension¹⁸. In a study of 6,834 adults, those who slept 6 or fewer hours per night were 1.7 times more likely to develop proteinuria than individuals who slept for 7 hours per night¹⁹ and in a small cross-sectional study of industrial employees, rotating shift workers had a higher prevalence of proteinuria relative to daytime only workers²⁰. We have preliminary data showing that short self reported sleep duration is associated with a more rapid decline in renal function independent of blood pressure and other factors (see, Preliminary Studies).

Sleep disruption and mechanisms for CKD: Decreased sleep duration, de-synchronization of sleep time, or fragmentation of sleep may cause renal damage through increased blood pressure (BP) and activation of RAAS,^{10,11,21-23} impaired glucose homeostasis,^{6,24} and endothelial dysfunction,^{25,26} all established risk factors for development of CKD.²⁷ Several studies have now demonstrated that acute (1-3 weeks) sleep deprivation increases insulin resistance, decreases pancreatic β islet cell function, and chronic sleep deprivation is a risk factor for development of diabetes.^{6,24,28} Similarly, short self-reported sleep duration and reduced measured SWS are associated with an increased risk of hypertension.^{17,18} Meanwhile, extension of sleep duration by 1 hour per night for 6 weeks has been found in small studies to decreased fasting insulin levels and brachial BP, suggesting sleep duration is a modifiable risk factor for CKD.^{29,30} However it was not clear if decreased fasting insulin levels were due to pancreatic β islet function or improved insulin sensitivity.

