We hypothesize that disruption of the sleep-wake cycle by sleep restriction increases risk for CKD, potentially via an increase in aldosterone secretion and reduction of nocturnal melatonin secretion with its pleiotropic effects on blood pressure, glucose metabolism, and endothelial function. We also hypothesize that correction of circadian disruption in high-risk, habitually sleep-restricted individuals by sleep extension or by melatonin supplementation using a controlled-release formulation administered at bedtime can reduce overall risk for CKD. These hypotheses give rise to the following specific aim:

1. Sleep extension and melatonin supplementation and CKD risk factors

In a 6 week pilot study, 20 individuals with habitual sleep restriction will all be asked to extend their nightly sleep by 1 hour, and will then be randomized 1:1 to nightly controlled-release oral melatonin (2mg) or placebo. We will assess whether sleep extension and nightly melatonin supplementation in the community is a feasible intervention with a beneficial effect on the following CKD risk factors: systemic and renal specific RAAS activation (systemic plasma renin activity, plasma angiotensin II

levels, 24-hour urine aldosterone excretion, and renal plasma flow response to captopril); nocturnal blood pressure measured by 24-hour ambulatory blood pressure monitor; central blood pressure measured by pulse wave analysis; and glucose metabolism measured by Minimal Model assessment of insulin resistance and β -cell response to a mixed meal protocol.

Subject Selection

An obese, pre-diabetic, pre-hypertensive population with habitual sleep restriction is ideally suited for a study of the effects of sleep extension and melatonin on CKD risk factors. We have shown that obesity and insulin resistance are associated with reduced endogenous melatonin secretion.^{39,64} Obesity predisposes individuals to aldosterone mediated inflammation and endothelial dysfunction. Thus, measures that reduce aldosterone secretion in these individuals may be particularly beneficial.^{10,23,65}

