Central Blood Pressure — Will be measured using pulse wave analysis using the SphygmoCor system (AtCor Medical, West Ryde, NSW, Australia), which measures central blood pressure and arterial stiffness.

Glucose metabolism — Will be evaluated by applying the Oral Minimal Model method to the results of a 2 hour 7- measurement, mixed meal tolerance test.² Subject will be given breakfast in the form of a mixed meal (10kcal/kg, 45% carbohydrate, 15% protein, 40% fat, 1g/kg glucose) which must be consumed within 15 minutes with glucose, insulin and c-peptide measured from arterialized blood drawn at 0, 10, 20, 30, 60, 90 and 120 minutes from start of meal. Glucose will be measured using a YSI glucose analyzer (CV <2%) for rapid measurement (YSI, Inc, Yellow Springs, OH), insulin will be measured with a radioimmunoassay (CV=10%) and c-peptide will be measured using an electrochemiluminescence

immunoassay(CV=12%). From the glucose, insulin and c-peptide measurements calculation of insulin sensitivity (reciprocal of insulin resistance) and β -cell responsiveness will be calculated.

Drugs to be used:

Captopril - The 25mg oral dose of captopril used during the renal specific RAAS measurement. Severe hypotensive reactions to a single dose of captopril are very uncommon in our experience among those we've studied who were free from pre-existing HTN, particularly in high sodium balance; nevertheless, participants will undergo constant monitoring during the RPF study, and the study will be stopped if the BP following captopril falls below 90 mmHg systolic or 50 mmHg diastolic, at which point the participant will receive medical treatment from the attending physician. Captopril may also be associated with angioedema, but typically occurs after repeated doses and even so the risk is <1%.

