Biostatistical analysis

The primary purpose of the trial is to generate pilot data for a larger randomized control trial.

Therefore we aim to calculate means and standard errors for the parameters as well as estimates of effects of sleep extension and melatonin supplementation which will allow accurate power calculations and facilitate the design of a larger study. While we suspect we will be underpowered in this study to find significant differences in endpoints due to sleep extension or melatonin supplementation we will perform statistical analysis on the outcomes as follows. For the main outcomes (renal specific RAAS, BP, glycemic control [insulin sensitivity and β -islet cell function]), we can assume a normal approximation for the changes in log transformed endpoints and so will use an ANCOVA analysis to compare the change in outcome from baseline to 6 week follow-up between melatonin (N=8) and placebo groups (N=8) of the study. Finally we will test the interaction of sleep extension and melatonin supplementation using multivariable linear regression of the parameter change with predictors which will include treatment assignments (sleep extension and melatonin supplementation) and the interaction term **sleep extension *melatonin supplementation** in an analysis of all study participants (N=16).

For the purposes of this grant we have performed power calculations for sleep extension based on either pilot data from obese individuals from our own studies or published results.

Renal specific RAAS Activity – Based upon published data, we assume that change in renal specific RAAS activity ($\Delta\text{RPF}_{\text{captopril}}$) is $46\text{ml}/\text{min}/1.73\text{m}^2$ in obese individuals, SD 12^{72} , and From these values, we estimate that we will have 80% power to detect a change in $\Delta\text{RPF}_{\text{captopril}}$ with sleep extension of $15\text{ml}/\text{min}/1.73\text{m}^2$ (33% from baseline) with type I error of 0.05 (two-tailed), **Table 7**.

Central Blood Pressure – Based on pilot data, we assume a mean central systolic BP of 106 mmHg and SD 10 mmHg with a between measurement correlation coefficient 0.89. Thus, for ANCOVA analysis the SD is 6.0 for change in BP. From these values, we estimate we will have 80% power to detect a change in BP of 8 mmHg due to sleep extension with type I error of 0.05 (two-tailed), **Table 7**.

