24 hour Ambulatory Blood Pressure – Based on pilot data, we assume a mean 24-hour systolic BP of 122.8 mmHg and SD of 10.4mmHg with a between-measurement correlation coefficient 0.74. Thus for ANCOVA analysis the SD is 5.0 for change in BP. From these values, we estimate that we will have 80% power to detect a 6 mmHg change in 24-hour mean SBP due to sleep extension with a type I error rate of 0.05 (two-tailed).

Insulin sensitivity –Based on published data, we assume a mean insulin sensitivity of 19.03 dl/kg/min/pmol/l and SD of 1.38 dl/kg/min/pmol/l and a between-measurement correlation coefficient of 0.7.^{2,73} Thus for ANCOVA analysis the SD for change in insulin sensitivity is 1.1 dl/kg/min/pmol/l. From these values we estimate that we will have 80% power to detect a change in insulin sensitivity of 1.4 dl/kg/min/pmol/l due to sleep extension with type I error of 0.05 (two-tailed), **Table 7**

β -islet cell responsitivity – Based on published data, we assume a mean β islet cell response (dynamic response, ϕ_d) of 494.88 and SD of 25.16 and a assume a measurement correlation coefficient of 0.7.^{2,73} . Thus for ANCOVA analysis the SD for change in ϕ_d is 17.68. From these values we estimate that we will have 80% power to detect a change in β islet cell response of 24 due to sleep extension with type I error of 0.05 (two-tailed), **Table 7**. All power calculation performed with PS power and sample size calculator, version 3.0.34.

Table 7: Comparison of the change in outcome we are powered to detect compared with measured changes in outcomes detected in other studies with lifestyle interventions or BMI comparisons.

Outcome	Intervention/Comparison	Δ Measured	Detectable change in this study
Renal Specific RAAS ⁷²	Obese vs overweight	9ml/min/1.73m ²	15ml/min/1.73m ²
Central systolic BP ⁴⁶	Diet and exercise	12 mmHg	8mmHg
24hour ABPM ⁴⁷	Difference in BMI of 5kg/m ²	3 mmHg	6mmHg
Insulin Sensitivity ²²	Diet and exercise	19% change	7% change
β -islet cell function ⁴⁰	Diet	20% change	5% change

Risks and Discomforts

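### The beta-cell function outcome is responsivity, which can fall when insulin sensitivity rises; the plan should add the disposition index and interpret beta-cell function on it

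*Combined protocol and SAP*

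**What the plan says.** Under Parameters Measured, the Glucose metabolism paragraph applies the Oral Minimal Model to a seven-sample mixed-meal test: "From the glucose, insulin and c-peptide measurements calculation of insulin sensitivity (reciprocal of insulin resistance) and" beta-cell responsiveness. No index combining the two is mentioned.

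The Biostatistical analysis section lists both as main outcomes under glycemic control and calls the second beta-islet cell function. The analysis is common to all main outcomes: "we can assume a normal approximation for the changes in log transformed endpoints and so will use an ANCOVA analysis". Each index is then powered separately. For sensitivity the plan claims "80% power to detect a change in insulin sensitivity of 1.4" on a mean of 19.03. For the dynamic responsivity index it assumes a mean "of 494.88 and SD of 25.16 and a assume a measurement correlation coefficient of 0.7". The SD of change "is 17.68. From these values we estimate that we will have 80% power to detect a change in" responsivity of 24. Table 7 shows these as detectable changes of 7% and 5%, the latter again labelled as beta-islet cell function.

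The Specific Aims ask whether the intervention "is a feasible intervention with a beneficial effect on the following CKD risk factors", and the list includes beta-cell response to a mixed meal. The Background, discussing earlier small sleep-extension studies, comments: "However it was not clear if decreased fasting insulin levels were due to pancreatic β islet function or improved insulin sensitivity".

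The plan contains no sensitivity-adjusted secretion measure, no joint analysis of the two indices, and no rule for reading a fall in responsivity.

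**The concern.** Responsivity measures how much insulin the beta cell releases for a given glucose stimulus. When the body becomes more sensitive to insulin, less secretion is needed, and responsivity can drop although the cell works as well as before. A change in responsivity therefore cannot be read as better or worse function until the change in sensitivity is taken into account. Improved sensitivity is one of the effects this trial looks for.

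The plan measures both parts but does not specify the step that separates them. That matters because the stated purpose of the pilot is to supply means, standard errors and effect estimates for designing a larger trial. If the quantity carried forward as beta-cell function is responsivity alone, the larger trial could be sized on a quantity that mixes function with compensation.

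**Working it through.** **Inputs (Biostatistical analysis and Table 7).** Sensitivity: mean 19.03, SD of change 1.1, detectable change 1.4. Dynamic responsivity: mean 494.88, SD of change 17.68, detectable change 24. Two-sided alpha 0.05, 80% power. Arm size is 8 in the Biostatistical analysis section and 10 under Potential Benefits.

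**1. The plan's own figure.** Two-sample t test, noncentrality = 24 / (17.68 × √(2/n)).
- n = 10 per arm: 24 / 7.91 = 3.04, 18 df, power 81.9%, detectable difference 23.4. The stated 24 reproduces.
- n = 8 per arm: 24 / 8.84 = 2.71, 14 df, power 71.4%, detectable difference 26.6.

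**2. Relative sizes.** 24 / 494.88 = 4.85%. 1.4 / 19.03 = 7.36%.

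**3. Fall in responsivity with function unchanged.** Assume responsivity is proportional to sensitivity^(−b). At b = 1 the product of the two stays constant, which is full compensation. The documents give no value of b, so a range is shown. For a relative sensitivity gain g:

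fall = 494.88 × (1 − (1 + g)^(−b))

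| b | g = 7.36% (plan's detectable gain) | g = 19% (Table 7, diet and exercise) |
|---|---|---|
| 1 | 33.9 | 79.0 |
| 0.75 | 25.7 | 60.5 |
| 0.5 | 17.3 | 41.2 |
| 0.25 | 8.7 | 21.1 |

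The fall equals 24 when b = −ln(1 − 24/494.88) / ln(1 + g). This gives 0.0497 / 0.0710 = 0.70 at 7.36%, and 0.29 at 19%. Against the t-based 26.6 for 8 per arm, the break-even at 7.36% is 0.0553 / 0.0710 = 0.78.

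**4. Which comparison is affected.** All participants extend sleep, so a sensitivity gain from sleep extension, and any compensating fall, is expected in both arms and largely cancels between them. Under b = 1, melatonin would have to raise sensitivity beyond placebo by 1 / (1 − 24/494.88) − 1 = 5.1%, or 0.97 units, to produce a between-arm fall of 24. The documents give no melatonin effect on insulin sensitivity. A pre-post estimate of sleep extension carries the whole shift.

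**5. Cost in precision of the product.** Relative SDs of change are 1.1 / 19.03 = 5.8% and 17.68 / 494.88 = 3.6%. If independent, the product's is √(5.78² + 3.57²) = 6.8%, which is 1.90 times that of responsivity. The detectable change moves from 4.85% to 4.85% × 1.90 = 9.2%. A negative correlation between the two changes reduces this. At an illustrative −0.5 the SD is √(5.78² + 3.57² − 5.78 × 3.57) = 5.1%, and the detectable change is about 6.9%.

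**The case against.** Several parts of the opposing case stand.

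- A reader might infer that the plan repeats the ambiguity it criticises. It does not. The criticism concerns fasting insulin, a single number. This plan takes both indices from one test, lists them together and powers each. A fall in responsivity would appear beside the rise in sensitivity that could explain it.
- A reader might infer that the effect size or sign passed to the larger trial would be wrong. The documents do not support that. Responsivity would be estimated correctly as responsivity, and the product could be computed later from participant-level data. What is missing is a prespecified way to interpret it as function.
- A reader might infer that a fall would be declared as harm. The plan states no favourable direction for responsivity, and the calculations are two-tailed. The label of function and the aim of a beneficial effect invite that reading but do not prescribe it.
- The compensation relation is general physiology that the documents do not state. Participants are obese and pre-diabetic, so full compensation cannot be presumed. At half compensation, the plan's detectable sensitivity gain gives a fall of 17.3, below 24.
- The 19% in Table 7 comes from diet and exercise, and the 1.4 is labelled as due to sleep extension. Neither is a melatonin effect.

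None of this removes the gap. Two indices reported side by side still leave the question of beta-cell function to be settled after the data are seen, with about 16 participants.

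**Conclusion.** The point holds as a recommended change. Dynamic responsivity alone does not answer whether beta-cell function changed, although the plan labels it so, and nothing prespecified links it to insulin sensitivity. At the plan's detectable sensitivity gain, unchanged function could appear as a responsivity fall of 17.3 to 33.9 units for b between 0.5 and 1. That exceeds the stated 24 only if b is about 0.70 or more (about 0.78 against the t-based figure for 8 per arm). The calculation rests on the assumed power relation and on a value of b that the documents do not give. Between arms it applies only to a sensitivity difference due to melatonin; for the pre-post sleep-extension estimate it applies in full. The claim that a compensating fall must exceed the detectable change goes further than the documents allow.

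**What to change.** In the Glucose metabolism paragraph and the Biostatistical analysis section:

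- Add the disposition index, insulin sensitivity × dynamic responsivity from the same model fit, as the measure on which beta-cell function is interpreted, higher being better. Analyse it on the log scale with the same ANCOVA. The change in log index is the sum of the two planned log changes; the ANCOVA estimate need not equal the sum of the two separate ANCOVA estimates, because the baseline covariates differ.
- Keep dynamic responsivity as a reported component, read only alongside insulin sensitivity.
- Report the mean and SD of change of the index for use in the larger trial.
- Next to the existing responsivity figure and in Table 7, state that the index has a relative SD of change of about 6.8% and a detectable change of about 9% if the components are independent, and less if they are negatively correlated.

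No sample, assay or visit is added. The cost is more than wording: the power paragraph and Table 7 need revising, and the index is noisier than responsivity, in a pilot that already expects to be underpowered.

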- Known obstructive sleep apnea or use of continuous positive airway pressure
- Insomnia
- Known allergy to melatonin
- Hypertension Type 1 or 2 (BP >150/90)
- Lactose Intolerance
- Autoimmune Disease

[figure not shown]
Subject Enrollment

Responders to advertisements will be pre-screened by telephone to obtain a BMI estimate and a medical history to gauge potential eligibility (**Table 5**). For those who may be eligible following this phone query, the basic study schema (**Figure 1**) will be described to identify those who remain interested in participation after learning the duration, inpatient requirements, and potential medication use. These individuals will then be invited to attend an outpatient screening visit.

We anticipate that the sex and race/ethnicity breakdown of subjects enrolled into EMC-PILOT will be similar to that which we have experienced in the MODERATE trial. Thus far in the MODERATE trial, enrolled subjects are 63% female, 28% black, 7% more than one race, and 13% Hispanic.

The pilot study is a double-blind, placebo-controlled randomized trial, in which 16 subjects with obesity (BMI \geq 30 kg/m²), pre-diabetes (HbA1C, 5.7-6.4%), and self-reported short sleep duration (<7 hours/night) are randomly assigned 1:1 to receive either placebo or 2 mg of controlled-release melatonin, taken orally every evening 1 hour before bed for 6 weeks. **All subjects will be asked to extend their sleep time by one hour** during the 6 week period between inpatient visits. Endpoints will be measured at both the baseline and 6-week inpatient visits.

Figure 1: Schema for pilot study with sleep extension and nightly melatonin as treatments.

Screening Visit: Screening visits will take place at the Brigham and Women’s Outpatient Center for Clinical Investigation (CCI; [name]). During the outpatient screen, [name] will explain the study in detail, review the consent form, and answer questions. After obtaining written informed consent for participation, a history and physical examination will be performed in order initially judge eligibility based upon the criteria set out in **Table 5**. Those individuals deemed potentially eligible based upon the screening history and exam will undergo phlebotomy and analysis for HbA1c, serum chemistries and glucose, and CBC to confirm eligibility using the criteria presented in the table.

[figure not shown]
Study Procedures

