Potential benefit to society: As described in detail in the **Study Procedure** section, we will perform a small pilot study of obese individuals. We plan to enroll a total of 20 individuals into a randomized controlled trial. All participants will be adults (age \geq 18 years), and will be recruited from the Boston area. Volunteers will be recruited and screened for inclusion based upon having a BMI \geq 30 kg/m², and having HbA1C between 5.7 and 6.4%. Other than having these “conditions”, potential participants will be expected to otherwise be in general good health, without severe co-morbid conditions as described in the **Subject Enrollment** section. There will be no involvement of special vulnerable populations. After randomization, participants will be retained by weekly phone calls; additionally, the duration of this trial (6 weeks) is relatively short. Study group assignment will be random, of the 20 participants, 10 will receive placebo, and 10 will receive controlled release melatonin (2.0mg of Circadin[®] nightly for 6 weeks). The 2 mg controlled-release formulation of melatonin has been studied previously in diabetic subjects and improves sleep duration. Pharmacokinetic data suggests that this dose of melatonin achieves nocturnal serum melatonin levels at or above physiological concentrations among healthy volunteers and is therefore adequate to replete nocturnal melatonin in individuals who have relatively low endogenous secretion.

The key potential benefit is the knowledge that is gained on potentially modifiable mediators of important pathophysiologic mechanisms of disease. The segment of the US population that would meet our study criteria is large; specifically, over half of the US adult population is obese, and nearly a quarter of these individuals have pre-diabetes. Thus, the results of this study could have profound public health implications.

Potential benefit to participants: It is possible that participants will gain direct benefit from these studies. First of all, it is possible that individuals who are not randomized to placebo will benefit from treatment. On the other hand, because this study is only 12-weeks in duration, these benefits (if present) will likely be short-lived.

Monitoring and quality assurance

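### The planned sample size is 20 in two sections and 16 in two others, nothing links the two figures, and Table 7 states no N

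*Combined protocol and SAP*

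**What the plan says.** Four sections give a sample size.

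- **Specific Aims, aim 1:** "20 individuals with habitual sleep restriction will all be asked to extend their nightly sleep by 1 hour, and will then be randomized 1:1". With 1:1 allocation this implies 10 per arm.
- **Potential Benefits:** "We plan to enroll a total of 20 individuals into a randomized controlled trial", and then "of the 20 participants, 10 will receive placebo, and 10 will receive controlled release melatonin".
- **Subject Enrollment (design paragraph):** a randomised trial "in which 16 subjects with obesity" and other entry criteria, who "are randomly assigned 1:1 to receive either placebo or 2 mg of controlled-release melatonin". This implies 8 per arm.
- **Biostatistical analysis:** the ANCOVA compares change "between melatonin (N=8) and placebo groups (N=8) of the study", and the interaction model is fitted "in an analysis of all study participants (N=16").

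For each of five outcomes, Biostatistical analysis then gives an SD, a detectable change, 80% power and a two-sided type I error of 0.05. Table 7 repeats the detectable changes. No N appears with any of these figures. Each detectable change is attributed to sleep extension, which every participant is asked to undertake, and not to melatonin.

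**The concern.** Both totals are presented as the number enrolled or randomised. Neither is described as a number of completers, and the analysis section calls its 16 all of the participants. The two figures therefore cannot both be right as written.

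The plan says its purpose is to produce means, standard errors and effect estimates for designing a larger trial, so N determines how precise the main product will be. The consent process must also tell participants how many people are expected to be enrolled (Adequacy of Protection Against Risks).

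Because the power text omits N, a reader cannot use it to tell which total was intended, or whether the stated 80% applies to the trial that will be run.

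**Working it through.** **1. The counts side by side**

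| Section | Total | Per arm |
|---|---|---|
| Specific Aims, aim 1 | 20 | 10 (implied by 1:1) |
| Potential Benefits | 20 | 10 (stated) |
| Subject Enrollment | 16 | 8 (implied by 1:1) |
| Biostatistical analysis | 16 | 8 (stated) |

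A 20% loss would turn 20 into 16 (20 × 0.8 = 16), but the documents state no such loss, and Subject Enrollment has the 16 being randomly assigned.

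**2. Effect on precision, in SD units**

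The standard error of the arm difference is SD × √(2/n).

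- n = 8: √(2/8) = 0.500 SD
- n = 10: √(2/10) = 0.447 SD
- Ratio: √(10/8) = 1.118, about 12% larger at 8 per arm

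The difference detectable with 80% power (two-sample t, two-sided 0.05, noncentral t with 2n − 2 df) is 1.51 SD at 8 per arm and 1.32 SD at 10. The unrounded ratio is 1.507/1.325 = 1.14.

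**3. Can the plan's 80% be reproduced?**

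Inputs are the stated SDs and detectable changes in Biostatistical analysis. Power comes from the noncentral t with noncentrality (Δ/SD) × √(n/2) for two arms, or (Δ/SD) × √n for a within-person (paired) test. Example, renal RAAS at 8 per arm: (15/12) × √4 = 2.50 on 14 df, giving 64%.

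| Outcome | Δ / SD | Two-sample, 8 per arm | Two-sample, 10 per arm | Paired, n = 8 |
|---|---|---|---|---|
| Renal RAAS | 15/12 = 1.25 | 64% | 75% | 86% |
| Central SBP | 8/6.0 = 1.33 | 70% | 80% | 90% |
| 24-h SBP | 6/5.0 = 1.20 | 61% | 72% | 83% |
| Insulin sensitivity | 1.4/1.1 = 1.27 | 66% | 77% | 87% |
| Beta-cell response | 24/17.68 = 1.36 | 71% | 82% | 91% |

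With the normal approximation instead of t, in the same order, two-sample power is 70.5, 76.0, 67.0, 72.1 and 77.5% at 8 per arm, and 79.8, 84.6, 76.5, 81.2 and 85.9% at 10. A paired test with n = 16 gives over 99% for all five.

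None of the sample sizes and formulas tried reproduces 80% for all five. On a between-arm reading the figures lie nearer to 10 per arm than to the 8 in the same section.

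**4. Do the change SDs follow from the plan's inputs?**

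For ANCOVA, SD × √(1 − r²):

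- Central SBP: 10 × √(1 − 0.89²) = 4.6, against 6.0 stated
- 24-h SBP: 10.4 × √(1 − 0.74²) = 7.0, against 5.0 stated

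Simple change scores, SD × √(2(1 − r)), give 4.7 and 7.5. With 4.6, the 8 mmHg central SBP change has about 90% power at 8 per arm (two-sample t). With 7.0, the 24-h change detectable with 80% power at 8 per arm is about 10.5 mmHg. The blood pressure rows in step 3 therefore depend on SDs that the plan's own inputs do not support.

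**5. Detectable changes at 8 per arm, melatonin versus placebo, stated SDs kept**

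1.507 × SD gives 18.1 ml/min/1.73m² (renal RAAS), 9.0 mmHg (central SBP), 7.5 mmHg (24-h SBP), 1.66 (insulin sensitivity) and 26.6 (beta-cell response).

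**The case against.** The strongest reply concerns power. The plan calculates power for sleep extension, which everyone receives, so the two-sample figures test a contrast that the power text does not name. Under a within-person reading with the stated SDs, even n = 8 gives 83–91%. The section also ties these calculations to a grant and reports no N with them, so they cannot be shown to rest on either total.

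This stands, and it rules out a stronger reading. A reader might infer that at 8 per arm none of the five stated changes has 80% power. The documents do not support that flatly: it needs a between-arm contrast and the stated SDs, and central SBP escapes it once its SD is derived from the plan's own correlation. Likewise, the count of outcomes reaching 80% at 10 per arm depends on the method: two by t, and four at or within rounding of 80% by the normal approximation.

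A second reply is that this is a pilot that expects to be underpowered, and a 12% change in standard error is modest. That limits the consequence, since no confirmatory claim depends on the power. It does not resolve the contradiction, because estimating standard errors is the stated purpose.

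A third is that 20 may have been meant to yield 16 completers. That is possible, but nothing in the documents says so.

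**Conclusion.** The contradiction is established by reading alone: 20 randomised in two sections, 16 in two others, with no rule joining them. It needs correcting whatever view is taken of power.

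Its size is about 12% on the standard error of the arm difference, and 1.51 against 1.32 SD on the difference detectable with 80% power.

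The power consequence is conditional. With a melatonin-versus-placebo contrast, the stated change SDs and a two-sample t-test, power for the stated changes is 61–71% at 8 per arm and 72–82% at 10, not a uniform 80%. On the within-person reading, with the same SDs, the shortfall does not arise.

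A reader might also infer that the plan intends a completers-only analysis. That would follow only if 20 are randomised and the 16 are completers, which the documents do not state.

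**What to change.** 1. State one randomised N, with the per-arm numbers, in Specific Aims, Subject Enrollment, Biostatistical analysis and Potential Benefits.
2. If 20 are to be randomised in the expectation of 16 completers, say so, give the assumed loss, and analyse everyone randomised.
3. Beside Table 7, state the N and the contrast: melatonin versus placebo, or within-person change under sleep extension.
4. Reconcile the two blood pressure change SDs with the stated SDs and correlations, then recompute Table 7 for the chosen N and contrast.

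The step 5 values (about 18 ml/min/1.73m², 9.0 mmHg, 7.5 mmHg, 1.66 and 27) should be used only if the contrast is melatonin versus placebo at 8 per arm and the stated SDs are kept. They must not then be labelled as effects of sleep extension.

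The cost is wording and possibly less favourable stated figures. No extra patients are needed.
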